A minimum of 93 participants (31 participants per group) aged 4-to-13 will be recruited through convenience sampling, consented, and randomized by staff to one-of-three preparation programs (VR, mock MRI, or booklet). Details of the comparison groups are outlined in **Table 4**. Given the restricted availability of the simulator, child life specialists, and the availability of participants, we are unable to fully randomly allocate participants. As such, participants will be randomly assigned to the intervention options available according to their individual availability (using Research Randomizer <https://www.randomizer.org/>). For example, if a participant is available on a Thursday that virtual reality and booklet are available, they will be randomly allocated to one of these interventions.

This phase will have open recruitment to all children and adolescents interested in participating, such that participants may not be BCCH patients scheduled for an MRI. This recruitment strategy was selected due to the resource constraints associated with limiting the evaluation group to MRI patients only.

Table 4. Details of the comparison groups.

	VR Simulation	MRI Preparation Booklet	Mock MRI
Facilitator	Research Assistant	Research Assistant	Child Life Specialist
Location	BCCH	BCCH	Simulation Room
Content	Refer to The Virtual Reality Simulation	Refer to MRI Preparation Book	Individualized intervention in physical simulator.

The different interventions will be held in separate private rooms located in BCCH, such that the VR and booklet groups will not have prior exposure to the imaging centre or the simulation room in advance of their assessment. This is to simulate our intended delivery in hospital, medical office, or clinic settings but minimize alternative explanations associated with testing in the simulation room where assessments will take place (previously described in **Table 3**).

Data will be collected throughout the implementation process (**Figure 3**). The predictive variables (demographics and relevant history, and delivery type) will be captured at the start of the session. The primary outcome variable is likelihood of success (pass/fail) of the MRI simulation, and will be measured at the end of the assessment. Anxiety will also be measured at three time points. Usability testing will be conducted throughout to capture possible quality improvements and amendments to each of the program delivery modes.

Inclusion/Exclusion Criteria

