Participants must be between the ages of 4-to-13 years to be included in the evaluation.

The following exclusion criteria, which have been noted in previous studies conducted using virtual reality programs, will be adopted for this project:

- mental disability (content not appropriate)
- significant visual and auditory impairment (this program focuses on auditory and visual cues)
- inability to speak or understand English (content and study staff are English speaking)
- history of seizures or epilepsy (triggered by virtual reality)
- facial or head wounds (cannot wear the virtual reality headset)

Implementation Plan

[figure not shown]

Figure 3. Implementation process.

The testing phase of the implementation process, depicted in Figure 3 will be completed over two hours, and will involve the following steps:

- 1) Participants and parents/guardians are greeted by staff and enter the intervention room.
- 2) Staff will obtain written consent from parents and verbal assent from children (5 minutes).
- 3) Participants will complete the Venham Picture Test (VPT) with staff (pre-test). In parallel, parents will complete the Short STAI on the iPad. (5 minutes)
- 4) Staff will reveal the allocated delivery mode (VR, mock MRI, or booklet) to the participant and explain the procedure.
- 5) Staff will ask participants to indicate on the Smileyometer how good they think the intervention is going to be.^{30,31} This will give a measure of expectation that can indicate whether or not the participant is subsequently let down by the activity or pleasantly surprised.
- 6) Staff will measure the participant's interpupillary distance using sliding calipers.
- 7) Participants will be given 45 active minutes to engage with the intervention. Groups include:

Group 1 (VR): The VR group will receive a virtual reality simulation designed during Phase 1 of this study.

Group 2 (mock MRI): The mock MRI will be provided by the CLS, according to the current care plan which consists of exposing children to the mock MRI, medical devices, and procedures. The mock MRI is located within the BCCH medical imaging facility.

Group 3 (booklet): The standard MRI preparation booklet group will provide access to a series of printed photos and text showing the MRI experience step-by-step to help prepare for the MRI.

- 8) Participants will be asked to indicate on the Smileyometer how good they actually thought the activity was overall (1 minute).

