- 9) Participants will be informed that they will now be completing a simulation test with the MRI scanner. Participants will be reminded of their free and informed ongoing consent.
- 10) The participant will be transferred to the simulation room, located in the medical imaging center at BCCH. Upon entering the simulation room, participants will verbally complete the VPT with staff (during test). In parallel, parents will complete the Short STAI on the iPad. (5 minutes)
- 11) Participants will be guided through a mock MRI and be assessed using MoTrack®, an objective head motion tracking system.³² The simulation will be completed over 20 minutes and will involve progression through the “MRI procedure”, remaining in the bore for 8 minutes. All participants will receive the same type of simulated scan. We will not be simulating any invasive procedures that can sometimes occur during the MRI (i.e. an IV or intravenous contrast liquid). Please note that this assessment involves a mock procedure using the simulator, not a real MRI.
- 12) Immediately following the simulation, participants will verbally complete the VPT with staff (post-test). In parallel, parents will complete the Short STAI on the iPad. (10 minutes).

- 13) Users will be asked to indicate on the *Smileyometer* how they thought the preparation activity was overall in preparing them for the MRI. Parents/guardians will be asked to complete the USE Questionnaire.
- 14) Staff will ask the user open-ended questions on the preparation materials according to three separate criteria of fun, ease of use, and how good it was for learning about the MRI experience. The final usability assessment will take a total of 10 minutes.
- 15) After the session is "complete", children will be told that they "happen to have some time left" so they can play with any of the preparation materials offered (VR, Mock MRI, Booklet) for 5-minutes if they want to "because they did so well during the activity." This will give children a natural choice selection and will be used to gauge preferences for the activities.
- 16) A verbal session debrief will include an opportunity for questions to mitigate any residual feelings of discomfort or anxiety that may arise from the project's activities.

Outcome Measures

The measures used to evaluate the intended outputs and outcomes associated with this project are outlined below (**Table 4**).

Table 4. Outputs and outcomes associated with the project.

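### Read literally, the plan takes the mock MRI arm's baseline anxiety in the simulation room before the reveal; the sections disagree, and baseline-dependent contrasts with that arm are at risk of bias

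*Combined protocol and SAP*

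**What the plan says.** All references are to section 4.4 of the combined protocol and SAP.

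- **Entry, step 1:** "Participants and parents/guardians are greeted by staff and enter the intervention room".
- **Baseline, step 3:** "Participants will complete the Venham Picture Test (VPT) with staff (pre-test". Parents fill in the Short STAI at the same time.
- **Reveal, step 4:** "Staff will reveal the allocated delivery mode (VR, mock MRI, or booklet) to the participant and explain the procedure".
- **Location row of the comparison-group table:** the mock MRI arm is in the "Simulation Room", with content described as "Individualized intervention in physical simulator". The VR and booklet entries name only the hospital.
- **Site of the simulator, step 7:** "The mock MRI is located within the BCCH medical imaging facility".
- **Safeguard below that table:** the interventions are held in separate private rooms, "such that the VR and booklet groups will not have prior exposure to the imaging centre or the simulation room in advance of their assessment". The stated reason is to limit rival explanations tied to testing in the simulation room. The mock MRI group is not mentioned.
- **Second measure, step 10:** each participant is first transferred to the simulation room, with no exception by arm. Then: "Upon entering the simulation room, participants will verbally complete the VPT with staff (during test".
- **Analysis and Interpretation:** a repeated-measures ANOVA with a within-between interaction of three anxiety time points and three delivery types. The pre-test is one of the three time points.

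**The concern.** Putting the pre-test before the reveal shows that a baseline free of knowledge of the arm was intended. The written room arrangements do not secure it for the mock MRI arm. No move is described between entering the intervention room and starting the intervention, and the mock MRI intervention takes place in the simulation room. Families in that arm could therefore give their first anxiety scores beside the scanner and already know their allocation.

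Any effect of the room on those scores would be tied to one arm. If it raised them, the mock MRI arm would show a smaller rise or a larger fall from baseline than the others, even with equally effective preparation. If it lowered them, the reverse would follow. Hypothesis 2b in section 4.2, no difference between VR and mock MRI, is exposed both ways: a shift could create a difference or hide one. The outcomes table lists both anxiety scales under its primary measures and counts participants and parents with reduced anxiety. Stage 2 of Phase 3 carries reductions in anxiety into the economic evaluation.

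**Working it through.** **1. Where the mock MRI baseline is taken**

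- *For the simulation room:* the safeguard describes each intervention as held in its own room, so the natural meaning of intervention room in step 1 is the room where that arm's preparation happens. For mock MRI, the table says this is the simulation room. No step moves the family between steps 1 and 7.
- *Against:* step 10 transfers everyone to the simulation room, which fits poorly with an arm already there. Step 4 would reveal nothing to a family beside the scanner.
- *Silent:* intervention room is not defined by arm, and no sentence says where the mock MRI pre-test is done. Figure 3 is not available in the text reviewed.

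The literal reading is a well-supported inference, not a stated fact.

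**2. What a shifted baseline does to the planned test**

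The plan gives no figure on this point to reproduce. From the plan: 3 arms, 3 time points, n = 31 per arm, α = 0.05. Assumed: common SD, equal between-time correlation ρ, normal scores, no true arm difference, and a shift of d SD in one cell (mock MRI, pre-test). A room effect common to all arms at the later time points is a time main effect and drops out of the interaction.

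For one shifted cell in a 3 × 3 table, the interaction terms are 4d/9 in that cell, −2d/9 in the four cells sharing its row or column, and d/9 in the other four. Their sum of squares is (16 + 4×4 + 4×1)d²/81 = 4d²/9.

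Noncentrality: λ = n × (4d²/9)/(1 − ρ), with (3−1)(3−1) = 4 and (93−3)(3−1) = 180 degrees of freedom.

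Example, d = 0.5 and ρ = 0.5: λ = 31 × 0.1111/0.5 = 6.89, which gives rejection in 52% of trials.

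| Assumed shift d (SD) | λ, ρ = 0.5 | False-positive rate, ρ = 0.5 | Range, ρ = 0.3 to 0.7 | 28 per arm, ρ = 0.5 |
|---|---|---|---|---|
| 0 | 0 | 5% | 5% | 5% |
| 0.1 | 0.28 | 6% | 6–7% | 6% |
| 0.2 | 1.10 | 11% | 9–16% | 10% |
| 0.3 | 2.48 | 20% | 15–32% | 18% |
| 0.5 | 6.89 | 52% | 38–77% | 47% |

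The last column applies the plan's 10% dropout (31 × 0.9 ≈ 28).

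**3. Change from baseline, mock MRI versus one other arm**

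The contrast moves by exactly d. The SD of a change is √(2(1 − ρ)) = 1 at ρ = 0.5, and the standard error of the difference is √(2/31) = 0.254. At d = 0.5 the ratio is 0.5/0.254 = 1.97, close to the critical value, so about half of trials reject. For d = 0.1, 0.2, 0.3 and 0.5 the rates are about 7%, 12%, 22% and 50%.

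**4. Baseline adjustment**

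Under the same assumptions the within-arm slope on baseline is ρ, so an adjusted comparison is still off by ρ × d. At d = 0.5 and ρ = 0.5 that is 0.25 SD. Adjustment shrinks the distortion but does not remove it, because the shift goes with the arm.

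**The case against.** The strongest reply is that the text never puts the mock MRI pre-test in the simulation room. The Location row may describe only where preparation is delivered. The universal transfer at step 10 and the order of steps 3 and 4 both suggest that every family starts somewhere else. This stands in part: the location is inferred, and actual practice may be sound. It does not settle the matter, because step 10 concerns the second measurement and nothing states where the first is made in this arm.

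A second reply is that the error rates come from an assumed shift. That stands. At 0.1 SD the rate is about 6%, barely above nominal. The Venham is a 0 to 8 count, and the effect of treating it as normal was not tested.

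A reader might infer more than the documents support:

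- *That the anxiety comparison is biased.* This needs both the literal reading and a non-zero room effect, and neither is established.
- *That VR and booklet baselines come from neutral rooms.* The plan says only that the rooms are separate and private. Whether they show arm-specific material is not stated.
- *That meeting the scanner for a second time at step 10 is itself a flaw.* Prior exposure is what the mock MRI preparation consists of.
- *That the whole trial is affected.* The MoTrak pass/fail result and direct between-arm comparisons of the during and after scores do not use the baseline. Scanner exposure does not touch VR versus booklet (hypothesis 2a), since both groups are kept away from the room.

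**Conclusion.** The concern holds as a conflict between sections and a risk of bias. The step order and the comparison-group table together place the mock MRI arm's baseline in the simulation room before the reveal, step 10 fits badly with that, and nothing protects this arm's baseline.

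If the literal reading is followed, the exposed results are change-from-baseline and time-by-arm contrasts involving mock MRI, including VR versus mock MRI and the anxiety reductions that Phase 3 draws on. The possible inflation runs from negligible at a 0.1 SD shift to about half of null trials at 0.5 SD, at correlation 0.5 and 31 per arm. These are conditional figures: the correlation and the size and direction of the shift are assumptions. The point is more than a missing detail, because a baseline taken in the wrong place cannot be collected again.

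**What to change.** Amend steps 1 to 4 so that all three arms complete consent, the pre-test Venham and Short STAI, and the reveal in one common room outside the imaging centre, with no arm-specific material in view. The mock MRI group then moves to the simulation room. Reconcile the Location row of the comparison-group table and step 10 with this, stating what the transfer at step 10 means for a group that has prepared there.

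The cost is a few sentences and one extra short walk for mock MRI families. Sample size and analysis are unchanged. Length of stay is unaffected: its clock starts only once staff have finished describing the intervention, and transition time is already excluded.

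The recruitment text speaks of a low enrolment rate, so enrolment may already have begun. If so, record where each earlier baseline was taken, flag participants tested before the change, and run a sensitivity analysis without their baseline-dependent results.

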Measure	Immediate Outputs	Intended Outcome
Primary		
MoTrak®	# of participants "prepared" to be scheduled for an effective MRI	
Improve access to MRI preparation for children who:
 
 - Live out of town - Would like to practice skills at home - Have mobility issues 
Improve non-sedation rates for MRI scans.

Venham Pictoral Test & Short STAI	# of participants with reduced anxiety # of parents with reduced anxiety	
Improve access to MRI preparation materials.
 
Improve behavioral compliance during medical procedures.

Secondary		
Smileyometer	# of participants who find the delivery mode fun and engaging to use	
Improve acceptability of preparation materials.
 
Improve satisfaction.

USE Questionnaire	# of parents who find the preparation materials useful	
Improve acceptability of preparation materials.
 
Improve satisfaction.

Natural Choice Selection	# of participants who select the booklet # of participants who select the mock MRI # of participants who select virtual reality # of participants who select none	Identify preference for engaging. Identify frequency of contact and time engaging.
Length of Stay	Minutes spent per segment	Improve hospital efficiency
Guided Survey	# of participants who find the booklet fun, easy to use, and good for learning about the MRI experience # of participants who find the mock MRI fun, easy of use, and good for learning about the MRI experience # of participants who find the virtual reality game fun, easy of use, and good for learning about the MRI experience	Improve utility of MRI preparation materials. Identify frequency of contact and time engaging.
Interpupillary Distance	Average interpupillary distance per age	Improve headset configuration.

Primary Measures

Predictive Success in Avoiding Sedation

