For the purposes of this evaluation, we will define total LoS as the duration, in minutes, from starting the *preparation* segment to completion of the simulated *assessment*. Inter-segment times will also be recorded. Preparation time will be capped at 45 minutes. Assessment time will be capped at 20 minutes. Start of preparation will be noted as time when study staff finish describing the intervention and indicate it is time to begin the active preparation. Time will stop when the participant is “discharged” from the MRI simulation, before the natural choice selection exercise and debriefing process begins. Time spent transitioning between activities or breaks required for reasons unrelated to the evaluation will not be counted towards overall LoS.

Interpupillary Distance

Interpupillary Distance will assume normal conditions and be measured objectively before preparation using Pryor's (1969) method³⁶ to ensure appropriate set up of the virtual reality device.

[figure not shown]

FIG. 1. Formula for interpupillary distance.

Usability Testing

The Smileyometer – 1 minute

The Smileyometer^{30,31} is an instrument used for measuring the opinions of technology in children, and has been validated in multiple studies assessing educational materials and software. The Smileyometer is based on the Visual Analogue Scale,³⁷ consisting of a 5-point Likert scale that uses pictorial representations. Participants are asked to point to the face they relate to.

Guided Survey – 10 minutes

The RA will ask the participant several open-ended questions on the preparation materials according to three separate criteria of fun, ease of use, and how good it was for learning about the MRI experience.

USE Questionnaire – 10 minutes

The USE Questionnaire²³ will be administered to the parents/guardians after the mock MRI only. This will allow participants to compare the VR application to the “effective MRI” experience. The USE Questionnaire is a 7-point Likert rating scale that has been well-validated to assess a program’s usefulness, ease-of-use, ease of learning, and satisfaction.

Analysis and Interpretation

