A priori power analysis was calculated using G-Power.³⁸ A total sample size (N) of 93 was calculated to be needed across the 3 groups (31 per group), with a significance level of 95% ($\alpha=0.05$) and a power of 90% ($\beta=0.10$), allowing for a 10% drop out rate. An effect size of 0.2 was selected to reflect the research suggesting that CLS preparation can reduce sedation rates by 20%.

Descriptive analysis will be conducted on the demographics and relevant history data.

Differences in predictive success of the MRI simulation ranking scores (pass or fail) will be examined using a Repeated Measures ANOVA, within-between interaction for three timepoint measurements (before, during, after) of anxiety and delivery type (VR, mock MRI, booklet). In the case of an off-normal distribution, non-parametric tests may be used. Multivariate analysis will test for possible confounding effects (demographics and relevant history).

Survey data (USE questionnaire, Smileyometer) will be analyzed using means and standard deviations of all respondents for each category of the questionnaires. The proportions of the participants reporting high, medium, or low levels will also be calculated.

Study staff will document responses to the guided survey and read the recorded answers back to participants to verify accuracy and elicit possible further reflection. All of the qualitative data will be uploaded to NVivo by study staff. When complete, study staff will code the information to identify major themes, gaps, barriers within the existing approach and the team will devise recommendations for improving the preparation programs. The phases of this process include:

- Familiarizing yourself with the data

- Generating initial codes
- Searching for themes
- Reviewing themes
- Defining and naming the themes
- Triangulation with other findings and producing a report

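### The Smileyometer is rated before and after preparation to show whether a child was disappointed or pleased, but only separate summaries are planned, so the number of such children is not obtained

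*Combined protocol and SAP*

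**What the plan says.** All references are to section 4.4 of the combined protocol and SAP.

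- **Implementation Plan, step 5.** After the allocated mode has been revealed at step 4, the child rates on the Smileyometer how good the activity is expected to be. The reason given is: "This will give a measure of expectation that can indicate whether or not the participant is subsequently let down by the activity or pleasantly surprised".
- **Implementation Plan, step 8.** After the preparation: "Participants will be asked to indicate on the Smileyometer how good they actually thought the activity was overall".
- **Implementation Plan, step 13.** After the simulated scan the Smileyometer is used a third time, with a different question: "how they thought the preparation activity was overall in preparing them for the MRI".
- **Usability Testing, The Smileyometer.** The instrument is described as "consisting of a 5-point Likert scale that uses pictorial representations".
- **Outcome Measures table.** The Smileyometer is listed as secondary. Its one output is the number "of participants who find the delivery mode fun and engaging to use".
- **Analysis and Interpretation.** "Survey data (USE questionnaire, Smileyometer) will be analyzed using means and standard deviations of all respondents for each category of the questionnaires". The next sentence adds: "The proportions of the participants reporting high, medium, or low levels will also be calculated".

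No other text deals with the analysis of the Smileyometer. The repeated measures ANOVA in the same section concerns the anxiety measurements and delivery type.

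**The concern.** Steps 5 and 8 form a pair of ratings within one child, and the reason given for step 5 is about that child: did the activity fall short of, or exceed, what he or she expected? Answering this requires the two ratings to be linked. Every summary named in the analysis text is marginal, meaning that it describes the ratings at one time without reference to the other time.

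What is at stake is modest. The usability work is meant to guide improvements to each preparation mode, and a mode that disappoints a third of its users calls for different action from one that disappoints none. Because expectation is asked once the child knows the mode, it may differ between arms. A step 8 rating alone cannot tell a well-liked activity from one that fell short of high hopes. If the summary is not set in advance, it will be chosen after the data have been seen.

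**Working it through.** The plan states no figure on this point, so there is none to reproduce. The check asks whether the planned summaries determine how many children rated lower, the same or higher at step 8 than at step 5. It takes the reading most favourable to the plan: each of the three Smileyometer ratings is summarised separately, and the same children answer at steps 5 and 8.

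**What can be recovered.** With complete pairs, mean(step 8 − step 5) = mean(step 8) − mean(step 5). The average shift therefore follows from the planned means. It follows by arm too if the means are split by arm, which the analysis text does not say.

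**What cannot: a two-value example.** Assumed ratings, not from the documents: half the children score 5 and half score 3, at both times.

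- Mean = (5 + 3)/2 = 4.0 and SD = 1.0 at both times. The high/medium/low proportions are also the same at both times, wherever the cut-offs lie.
- Let p be the share going from 5 to 3. Equal distributions at the two times force the same share p to go from 3 to 5. The share unchanged is 1 − 2p.
- Each rating lies 1 above or 1 below the mean, so the within-child correlation is r = (1 − 2p) − 2p = 1 − 4p. Hence p = (1 − r)/4.

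| Correlation r | Share lower at step 8 |
|---|---|
| +1 | 0% |
| 0.5 | (1 − 0.5)/4 = 12.5% |
| 0 | 25% |
| −1 | 50% |

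The average shift is 0 in every row, and every planned summary is identical.

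**A five-point example at the planned group size of 31.** Again the ratings are assumed.

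- Step 5: 5 twos, 8 threes, 10 fours, 8 fives. Mean = (10 + 24 + 40 + 40)/31 = 114/31 = 3.68, SD 1.05.
- Step 8: 3 twos, 8 threes, 10 fours, 10 fives. Mean = (6 + 24 + 40 + 50)/31 = 120/31 = 3.87, SD 0.99.
- Low/medium/high, with assumed cut-offs 1–2, 3 and 4–5: 5/8/18 at step 5 and 3/8/20 at step 8.

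These are all the planned summaries. Two ways of pairing the same ratings give:

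| Pairing | Lower | Same | Higher | Mean change | SD of change |
|---|---|---|---|---|---|
| Same rank order | 0 | 25 | 6 | 0.19 | 0.40 |
| Reverse rank order | 11 | 7 | 13 | 0.19 | 1.97 |

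The mean change is 6/31 = 0.19 in both. The number rating lower is 0 of 31 or 11 of 31. The SD of the change also differs, so the separate SDs do not give a confidence interval for the average shift either.

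**The case against.** The strongest reply is that step 5 gives a reason for asking the question and does not promise a result. It says what the rating can indicate. Disappointment or surprise is not an output in the Outcome Measures table, nor an objective or hypothesis in section 4.2. The preference hypothesis has its own measure, the natural choice selection. The data are collected in any case, so the change can be computed later. All of this stands, and it is why the point is minor. It does not supply the missing summary: a reason that concerns the individual child is given, and no planned analysis serves it.

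Several stronger readings are tempting but not supported.

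- A reader might infer that means and SDs are all that is planned. They are not: proportions at three levels are also planned. These are marginal too, so they do not close the gap.
- A reader might infer that the plan can say nothing about expectation against experience. It can, for the group average.
- A reader might take 50% as the likely size of the problem. It requires every child to swap scores, at correlation −1. At any correlation of zero or above, the same example gives 0% to 25%.
- A reader might infer that the plan loses precision by treating the two ratings as unrelated. It plans no standard error, interval or test of their difference, so there is no such error.

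**Conclusion.** The point holds in a limited form. The Smileyometer analysis gives the distribution of ratings at each time and, by subtraction, the average shift. It does not give how many children rated the activity below or above their own expectation, which is the reason stated for the step 5 rating. In the two-value example the share rating lower runs from 0% to 50% under identical summaries, and is 12.5% at correlation 0.5. In the 31-child example it is 0 or 11 children. All these ratings, correlations and cut-offs are assumed; the documents give no Smileyometer data. The examples show that the answer is not determined by the planned summaries, and they do not predict what this trial will find.

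A reader might go further and infer that a declared endpoint goes unreported or that the trial's main conclusions are weakened. The documents do not support that: the measure is secondary, this comparison is not a listed output, and neither the primary outcome nor the sample size depends on it.

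**What to change.** In Analysis and Interpretation, add the within-child change, step 8 minus step 5.

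- Report by arm the number and percentage of children rating lower, the same and higher. This suits a five-point pictorial scale better than a mean change alone.
- Add a paired ordinal summary within arm, such as the Wilcoxon signed-rank.
- Show separately the children already at the top score at step 5. They cannot rate higher afterwards, so an arm with high expectations has less room to improve.
- Keep the step 13 rating out of this comparison, because it asks how well the activity prepared the child.
- Label any comparison of the change between arms as descriptive, since no hypothesis names it.

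The cost is one derived variable and one table. No new data, visits or participants are needed.
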